7.4 Definition of the Secondary Outcome Measures

The secondary outcomes of this study are to determine the efficacy of up to 30 sessions of rTMS versus up to 30 sessions of sham rTMS for treatment of CUD or MUD, separately. The secondary outcomes will be determined assessing the percentage negative of the last UDS per study week (target 7-day period including visit windows) over the 8-week treatment period in the participant's respective primary use designation at randomization.

Urine drug screens will be collected at each treatment session prior to the rTMS or sham treatment during the treatment period and tested for substances including cocaine and methamphetamine. All UDS must be within temperature range and unadulterated to be a valid outcome measure. Primary substance of use is defined for the substance designated on the enrollment form (ENRC) on the day of randomization. If UDS was 1) collected at multiple screening visits, 2) collected at the final screening visit on the day of randomization (i.e., an earlier UDS is being used as baseline) and 3) not collected again after randomization before the same-day treatment session, the UDS may be used as a Week 1 result. If two UDS are collected on the last day of the study week, the last UDS collected will be used, as designated by the visit number. UDS collected at the EOT visit may be the last UDS collected during the treatment period and contribute to the secondary outcome if it is within the treatment period window (up to and including Day 63). If a participant ends treatment early, the EOT UDS will contribute to the study week based on 7-day periods from day of randomization.

The hypotheses are that individuals who receive active rTMS will have a significantly higher percent UDS negative results for methamphetamine (if participants are designated in the primary MUD group), or cocaine (if participants are designated in the primary CUD group) over the course of treatment, as compared to those in the sham group.

7.5 Analyses of the Secondary Outcome Measures

The secondary (efficacy) outcome will be analyzed in the ITT population (defined in Section 3.1.3) with a generalized linear mixed model approach to adjust for correlation between UDS from the same participants and to provide conditional interpretation of the treatment effect. The model will include fixed effects for treatment, major depressive episode (MDE), week, and site and a random effect for participant. It is important to note that a repeated measure, binary response of negative UDS, for each UDS provided by each participant, will be used as the outcome, as opposed to the total percentage of negative UDS. The model used still allows inference on the overall probability of a negative weekly UDS during the treatment period. Additionally, week will enter the model as a categorical variable to allow greater flexibility on the effect of week. Section 7.9 describes missing data handling procedures for the secondary outcome sensitivity analyses.

The assessment of the significance of the treatment will be done by testing the significance of the treatment parameter at the 0.05 significance level. The treatment effect will be measured by an odds ratio with an associated 95% confidence interval. The corresponding SAS code is provided below:

```
proc glimmix data = data method = quad;
  class site week participant;
  model y(event = '1') = trt mde week site / dist = binary link
    = logit solution;
  random intercept / subject = participant;
run;
```

where:

- data is a dataset with one row per weekly UDS per participant for the specified primary substance of use,
- y is the binary variable with a value of 1 indicating the UDS for that participant was negative and 0 indicating positive UDS result,
- trt is a binary variable with a value of 1 indicating active rTMS and 0 indicating sham rTMS,
- mde is a binary variable with a value of 1 indicating the presence of MDE,
- week is the study week (1 – 8, categorical), and
- site is a categorical variable containing which of the sites each participant was enrolled in.

In the event that the estimate of the variance component related to the within participant correlation (i.e., the ICC for UDS) is so close to 0 that it causes the overall covariance matrix to not be positive definite, the model will be refit without the random effect for the correlation within participant. This is accomplished simply by removing the random effect.

An odds ratio (as the exponential of the trt coefficient), along with 95% confidence interval, will be provided to assess the effect of treatment. An odds ratio of greater than 1 would indicate an increased odds of a negative weekly UDS for active rTMS versus sham rTMS during the treatment period. That is, a positive effect of rTMS versus sham. Similarly, a value of less than 1 indicates a decreased odds of a negative weekly UDS for active rTMS versus sham rTMS during the

treatment period. That is, a negative effect of rTMS versus sham. A p-value will also be provided to test the significance of the effect.

The model and results will be conducted and presented separately for those participants randomized with CUD or MUD.

Secondary outcome availability and UDS results negative for cocaine and methamphetamine separately as defined by primary substance of use will be summarized by study week, by site, and by treatment arm. A summary of the secondary outcome analysis will be provided by treatment arm separately for each primary substance of use and will include the odds ratio and 95% confidence interval. A forest plot will also be provided.

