12.0 STUDY ASSESSMENTS

12.1 Overview

Study assessments were chosen to help understand the feasibility and effects of rTMS on individuals with stimulant use disorders. The assessments for this study balance the value of comprehensive data against feasibility and participant burden. Screening will evaluate full eligibility, including diagnosis of CUD and/or MUD and other psychiatric diagnoses. The study clinician must review and approve all safety and eligibility assessments to confirm participant eligibility prior to randomization. Excluding collection of study participant characteristics and locator information, the participant baseline data will include past alcohol and drug use including cocaine and methamphetamine using the Timeline Follow-Back (TLFB) method, use of other substances, quality of life, and other data chosen to evaluate the efficacy of rTMS in stimulant users (e.g., sleep). Table 5 provides a listing of administrative/data collection forms, and Table 6 includes the schedule for study specific assessments and procedures.

Table 5: Administrative Forms/Data Collection

	SC	RND	Double-Blind Treatment Phase								Post	FU	FU
Study Week	0	0	1	2	3	4	5	6	7	8	EOT	12	16
Pre-Screen Summary	X												
Randomization Enrollment Form	X												
Daily rTMS Treatment Log			X	X	X	X	X	X	X	X			
Visit Documentation			X	X	X	X	X	X	X	X	X	X	X
Protocol Deviation Form	-	-	-	-	-	-	-	-	-	-	-	-	-
End of Treatment Form											X		
Study Completion													X
Mental Health Assessment Follow-up	-	-	-	-	-	-	-	-	-	-	-	-	-
Serious Adverse Event Summary	-	-	-	-	-	-	-	-	-	-	-	-	-
Inventory Medication and Supplies	-	-	-	-	-	-	-	-	-	-	-	-	-
Actigraph Device Discontinuation			-	-	-	-	-	-	-	-	X		
EEG Completion (if available)			X			X							

- Completed as necessary

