12.7 Substance Use Assessments

12.7.1 Timeline Follow-Back (TLFB)

The Timeline Follow-Back (Sobel & Sobel, 1992) procedure will be used to elicit the participant's self-reported use, quantity, and route of administration of substances at baseline, throughout the treatment period, and at end of treatment and follow-up assessments. At screening, this form will be used to assess substance use for the 30-day period prior to screening. The TLFB will be administered throughout the active treatment phase and through the end of the follow-up period to document the participant's self-reported use of substances for each day since the previous TLFB assessment. We plan to use the TLFB to track self-reported use of all substances. At the 12- and 16-week post-randomization follow-up, substance use is reported since the last visit.

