random effect from a normal distribution was added to the logit of the probability value used to generate the number of negative UDS for each participant, with fixed standard deviation. The standard deviation used was determined based on a small set of possible within-participant correlation, or intraclass correlation (ICC), values. Specifically, ICCs of 0.25 and 0.5 were considered, relating to standard deviations of about 1.05 and 1.81 respectively based on the latent variable method of Goldstein, Browne, and Rasbash 2002.

Once the dataset was simulated, a mixed effect logistic regression model was fit with only binary treatment (1 for real rTMS), binary stratum, week, and site as fixed effects and a random effect to account for correlation between UDS from the same participant. Each weekly UDS enters the model as a binary response. If the model estimation procedure had issues with not being positive definite, the model was refit with the random effect removed. Once the model was fit, it was determined whether the treatment covariate was significant or not at the 0.05 confidence level (i.e., if the p-value was less than 0.05). If the covariate was significant, the treatment effect was considered significant. This process, along with data generation, was repeated 10,000 times. The proportion of times the treatment effect was considered to be significant was the power. A power of at least 80% was desired.

[figure not shown]
The power to detect a significant treatment effect decreases as treatment effect size and sample size decrease. To this end, the simulation study also considered other sample sizes (40, 60, and 100) and different treatment effect sizes, with the highest odds ratio being 5 and the lowest being 2, a clinically meaningful level. Note that this range of odds ratios is below the estimate found in Terraneo et al. (2016), (of 6.5) for a similar outcome. As previously mentioned, differing proportions in the sham rTMS arm are also considered to gauge the sensitivity of the results to the assumption of 0.36, specifically 0.26 and 0.46 were also considered.

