15.3.2 Secondary (Efficacy) Outcome

The secondary (efficacy) outcome will be analyzed with a generalized linear mixed model approach to adjust for correlation between UDS from the same participants and to provide conditional interpretation of the treatment effect. The model will include fixed effects for treatment, MDE, week, and site and a random effect for participant. It is important to note that a binary response of negative UDS, for each UDS provided by each participant, will be used as the outcome as opposed to just their percentage of negative UDS. The model used still allows inference on the overall probability of a negative weekly UDS during the treatment period. Additionally, week will enter the model as a categorical variable to allow greater flexibility on the effect of week.

The assessment of the significance of the treatment will be done by testing the significance of the treatment parameter at the 0.05 significance level. The treatment effect will be measured by an odds ratio with an associated 95% confidence interval. The corresponding shell SAS code is provided below.

```
proc glimmix data = dat method = quad;
  class site week participant;
  model y(event = '1') = trt mde week site / dist = binary link
  = logit;
  random intercept / subject = participant;
run;
```

dat is a dataset with one row per weekly UDS per participant. y is the a binary variable with a value of 1 indicating the UDS for that participant was negative, trt is a binary variable with a value of 1 indicating real rTMS and 0 indicating sham rTMS, mde is a binary variable with a value of 1 indicating the presence of MDE, week is the study week, and site is a categorical variable containing which of the sites each participant was enrolled in.

In the event that the estimate of the variance component related to the within participant correlation is so close to 0 that it causes the overall covariance matrix to not be positive definite, the model will be refit without the random effect for the correlation within participant. This is accomplished simply by removing the line starting with random in the shell SAS code shown above.

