3.2.5 Baseline Value

The baseline value for each assessment will be considered the last non-missing value collected during screening prior to randomization, except for:

- 1) substance use (urine drug screen) which is defined as the first UDS collected during screening, and
- 2) the following assessments which may be collected after randomization and before the first treatment session:
 - Cue Craving Assessment (CCA, first pre-cue, pre-treatment exposure question only)
 - EEG Completion (EEG)

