11.0 INTERIM ANALYSES AND DATA MONITORING

11.1 Sample Size Re-Estimation

There was no planned sample size re-estimation. In October 2022, the NIDA CCTN requested a sample size re-estimation due to slower than expected recruitment. The precision analysis related to the primary (feasibility) outcome was repeated for additional sample sizes of $N = 60, 100, 110, 130, 140$, and 150 under the previously assumed feasibility metrics of 50%, 60% and 75% of participants randomized will receive 20 or more sessions.

The power analysis for the secondary (efficacy) outcome was repeated with the following parameters updated utilizing data from the observed sham treatment arm:

1. The average standard deviation of UDS results was estimated to update the parameter for the correlation between UDS from the same participant. Both treatment arms were used to estimate the ratio as this does not explore the treatment effect and therefore would not impact Type I error.
2. The probability of success was estimated based on observed sham treatment arm data across primary use subgroups due to small observed sample size at the time of data freeze and to preserve the blind. Note that only data from the sham treatment arm was used to protect the double blind. Additionally, no knowledge of the treatment effect was gained and no adjustments for Type I error would need to be made.
3. A smaller treatment effect (odds ratio = 1.5) was included. As noted in the protocol, an odds ratio of 2.0 is considered clinically meaningful.

An additional sample size re-estimation was requested by NIDA CCTN and conducted in December 2023 following the same methods. All analyses during both rounds were performed by blinded DSC statisticians.

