	120	0.086
	130	0.083
	140	0.080
	150	0.077
	160	0.075
75%	200	0.067
	400	0.048
	40	0.128
	60	0.106
	80	0.093
	100	0.083
	110	0.080
	120	0.076
	130	0.073
	140	0.071

Table 5: Re-estimation Power Analysis Results for Secondary (Efficacy) Outcome

		Power n per Use Disorder Subgroup	
Probability of Negative UDS in Sham Arm	Odds Ratio	n = 50	n = 70
-0.025	1.5	14%	13%
	2.0	25%	36%
	3.0	67%	82%
Observed Probability	1.5	15%	20%
	2.0	42%	56%
	3.0	86%	96%
+0.025	1.5	19%	27%
	2.0	54%	70%
	3.0	95%	99%

The second sample size re-estimation conducted in December 2023 followed the same methods with current data used to estimate the UDS standard deviation and probability of success. The report provided to NIDA CCTN February 13, 2024 contained the following results:

1. The target sample size in each use disorder group required in order to detect clinically meaningful effect size of 2.0 with at least 80% power is 92.
2. With 52 participants, the number of participants recruited in the cocaine use disorder group as of database freeze December 15, 2023, there is at least 80% power to detect an odds ratio of 3.0.

It was determined that with the number of participants recruited in each use disorder group, assuming the recruitment rate in that group as of late December 2023, it would take approximately 14 months to achieve the sample size in the cocaine use disorder group to be able to detect the clinically meaningful effect size. The protocol was not amended, and NIDA CCTN recommended the study recruitment not be extended.

Table 6: Power to detect OR=2.0 for various sample sizes

N per Group	Power
52	53.1%
80	73.2%
90	79.4%
91	79.7%
92	81.6%

Table 7: Power for n=52 and various odds ratios and probabilities of a negative UDS

Probability of Negative UDS	Odds Ratio	Power
-0.025	2	40%
	3	85%
Observed	2	53%
	3	94%
0.025	2	63%
	3	97%

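### The supportive efficacy fits that pool CUD and MUD omit the primary-substance stratum, which can overstate the standard error; the efficacy model also omits baseline use, at an uncertain cost in precision

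*SAP*

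**What the plan says.** SAP 7.5 fixes the terms of the efficacy GLMM: "The model will include fixed effects for treatment, major depressive episode (MDE), week, and site and a random effect for participant". Protocol 15.3.2 agrees: "The model will include fixed effects for treatment, MDE, week, and site and a random effect for participant". Both documents run the main analysis separately for CUD and MUD. SAP 2.2.4 stratifies randomisation by site, current MDE and primary substance. In the main fits all three strata are therefore respected: two as terms, the third by separate fitting.

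SAP 7.6.2 then repeats the analysis on the two groups together. Item 2 takes everyone randomised, with three outcomes: (a) negative for all substances, (b) negative for stimulants, (c) negative for the participant's own primary substance. Item 3 takes participants who reached 20 sessions, by substance and overall. No CUD/MUD term is named for any pooled fit.

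On baseline use, Protocol 12.7.1 says of the Timeline Follow-Back (TLFB): "At screening, this form will be used to assess substance use for the 30-day period prior to screening". Protocol 12.1 says "the participant baseline data will include past alcohol and drug use including cocaine and methamphetamine using the Timeline Follow-Back (TLFB) method". SAP 3.2.5 also defines a baseline value for "substance use (urine drug screen) which is defined as the first UDS collected during screening". None of these enters the model.

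SAP 7.10 records that after database lock the planned models could not be completed. SAP 7.10.1 falls back to treatment plus a random participant effect, then to summary statistics.

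**The concern.** Primary substance is the one randomisation stratum that disappears when the groups are pooled. If CUD and MUD participants give negative screens at different rates, that difference is pushed into the participant random effect. The model then treats it as noise between arms, although stratified allocation has largely removed it from the comparison.

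Baseline use is a natural predictor of later urine results, and it is already collected. The pilot is meant to supply an effect size for later trials, so the width and calibration of its intervals are part of what it delivers.

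**Working it through.** **1. Reproducing the plan's power.** Inputs from Protocol 15.2.2 and SAP 10.2: 80 per group, 1:1 allocation, 8 screens each, sham probability 0.36, two-sided 0.05. On the variance, the Protocol says: "Specifically, ICCs of 0.25 and 0.5 were considered, relating to standard deviations of about 1.05 and 1.81 respectively". These follow from SD = √[(π²/3)·ICC/(1−ICC)]: √(3.29/3) = 1.05 and √3.29 = 1.81. Method: simulate logit(p) + log(OR)·treatment + N(0, SD²), fit a random-intercept logistic model by Gauss–Hermite quadrature, and apply a Wald test.

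| Power at OR 2/3/4/5 | Stated | Simulated |
|---|---|---|
| ICC 0.25 | 67/96/100/100% | 65/96/100/100% |
| ICC 0.5 | 35/69/86/94% | 34/68/86/93% |

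The simulation model matches the plan's.

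**2. Pooled fits: mechanism.** Take 80 + 80 participants, CUD sham rate 0.36 and an assumed MUD sham rate of 0.10. The logits are −0.575 and −2.197, a gap of 1.622. With equal halves this adds (1.622/2)² = 0.658 to the random-intercept variance. At ICC 0.25 the SD becomes √(1.05² + 0.658) = 1.33. The simulated median was 1.33 without the substance term and 1.03 with it.

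**3. Pooled fits: results** (1,500 replicates per cell; each pair is without → with the substance term).

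| ICC | CUD/MUD rate (assumed) | Type I error | Power at OR 2 | Mean model SE at OR 2 | Empirical SD at OR 2 |
|---|---|---|---|---|---|
| 0.25 | 0.36/0.36 | 4.9 → 5.1% | 92.6 → 92.8% | 0.209 → 0.209 | 0.208 → 0.208 |
| 0.25 | 0.36/0.26 | 4.4 → 4.9% | 89.6 → 90.1% | 0.214 → 0.210 | 0.214 → 0.214 |
| 0.25 | 0.36/0.10 | 1.8 → 4.6% | 79.7 → 87.4% | 0.260 → 0.221 | 0.220 → 0.220 |
| 0.25 | 0.36/0.05 | 1.0 → 5.6% | 63.2 → 84.3% | 0.309 → 0.234 | 0.230 → 0.229 |
| 0.5 | 0.36/0.36 | 5.3 → 5.4% | 56.9 → 57.0% | 0.326 → 0.325 | 0.323 → 0.323 |
| 0.5 | 0.36/0.10 | 3.1 → 4.7% | 48.5 → 54.3% | 0.361 → 0.335 | 0.341 → 0.337 |
| 0.5 | 0.36/0.05 | 3.7 → 5.9% | 41.3 → 54.3% | 0.400 → 0.346 | 0.353 → 0.347 |

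Simulation error on a 5% rejection rate is √(0.05·0.95/1500) ≈ 0.6 points. A further set of simulations at 0.36/0.10, ICC 0.25, under no effect gave a model SE of 0.263 against an empirical SD of 0.219 (type I error 1.2%), and 0.225 against 0.220 (3.9%) with the term. The estimate itself hardly changes: the median OR at a true OR of 2 stays at 1.96–2.03 throughout. The reported SE is what goes wrong.

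**4. Baseline use, planning variances.** Let the covariate carry a share ρ² of the random-intercept variance. The documents give no ρ, so it is assumed. N = 80, p = 0.36, OR 2:

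| ρ | SE fall, ICC 0.25 | SE fall, ICC 0.5 |
|---|---|---|
| 0.2 | 1.4% | 1.5% |
| 0.3 | 3.1% | 3.5% |
| 0.5 | 8.2% (0.294 → 0.270) | 10.1% (0.457 → 0.411) |
| 0.7 | 16.7% | 21.2% |

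At ρ = 0.5, power moves from 65.5 to 73.3% and from 32.6 to 39.6%.

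**5. Baseline use, updated inputs.** SAP 11.1 replaced the planning variance: "The average standard deviation of UDS results was estimated to update the parameter for the correlation between UDS from the same participant". The second round, in SAP 11.1.1, worked "with current data used to estimate the UDS standard deviation and probability of success". Neither estimate is printed. SAP Tables 6 and 7 give, at n = 52, 53.1% power at OR 2 and 94% at OR 3. With SE = ln(OR)/(1.96 + z_power), these imply 0.693/(1.96 + 0.078) = 0.34 and 1.099/(1.96 + 1.555) = 0.31. Assumed inputs p = 0.08, SD 0.4 give 43/53/61% at OR 2 (stated 40/53/63%), 94% at OR 3 (stated 94%), and 74% at OR 2 with n = 80 (stated 73.2%). There, at ρ = 0.5, two sets of runs gave SE 0.335 → 0.336 and 0.339 → 0.340: no gain. An SD of 0.4 leaves a between-participant variance of only 0.16 to explain. Nearby inputs range from a 0.8% rise (p = 0.07, SD 0.2) to a 2.0% fall (p = 0.08, SD 0.6).

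**6. Missing screens.** Steps 1–5 use complete data, but SAP 7.9 expects missing UDS. In illustrative scenarios with a true OR of 1 and 30% or 60% of heavier users lost in the active arm only, the estimated OR was 1.04–1.14 without the term and 1.02–1.03 with it when loss followed week 2. It was 1.05–1.56 and 0.98–0.99 when those users gave no screens at all.

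**The case against.** No passage promises baseline adjustment, so leaving it out contradicts nothing. The inputs that best match the updated tables show no gain from it, and the entry rule of at least 10 use days in 30 narrows the covariate. SAP 7.10 says the planned model could not be completed, so an extra term may have nowhere to go. All of this stands, and it reduces the baseline-use point to a secondary one.

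On the pooled fits, the power section gives both substances the same 0.36, at which nothing changes. The strongly different rates are assumptions. Items 2a and 2b use one outcome for everyone, so a gap in primary-substance rates need not carry over. These analyses are supportive only. That limits the size but does not answer the point: SAP 7.5 includes the other two strata, and SAP 7.6.2 gives no reason to drop the third.

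A reader might infer that the main CUD and MUD results ignore a stratification factor, or that the unadjusted intention-to-treat test is invalid. Neither follows: the main fits are separate by substance, and lack of baseline adjustment does not invalidate a randomised comparison.

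**Conclusion.** Both omissions are certain; their consequences differ.

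The pooled fits are the main point. When the two groups' negative rates differ strongly, the model overstates the SE and the test is conservative. At assumed rates of 0.36/0.10 and ICC 0.25, type I error is about 1–2% without the term and 4–5% with it. Power at OR 2 is about 80% against 87–89% across the two sets of simulations. At equal rates there is no effect. These figures assume 80 per group, balanced arms within substance and complete data. Item 3's overall test selects on sessions received, so that balance need not hold there.

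Omitting baseline use costs precision with complete data: about 8–10% of the SE at an assumed correlation of 0.5 under the planning variances, and about zero under inputs close to the updated tables. Confidence in the size is low.

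Two stronger readings are tempting. One is that omission biases the treatment odds ratio. With complete data it does not; bias needs missingness tied to both baseline use and arm, and the documents report no such pattern. The other is that the loss is purely one of precision. That is too narrow, because the pooled problem is a miscalibrated SE and missing UDS could add bias. The point is worth considering but is not critical.

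**What to change.** Add CUD/MUD as a fixed effect in every fit that pools the groups (SAP 7.6.2 items 2a–c and the overall test in item 3). Where the full 7.5 model can be estimated, add screening TLFB days of primary-substance use as a continuous covariate. Count primary-substance days only, because the entry criterion accepts days of either drug.

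SAP version 2.0 post-dates database lock, so report both as post hoc sensitivity results beside the prespecified ones, not in their place. Do not require the TLFB covariate in the simplified model of 7.10.1.

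The cost is one model term and one sentence for each change, using data in hand. The downside is one extra parameter per model, which may not be estimable in sparse UDS data, and an SE rise of under 1% if the covariate carries little information.
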